This study is a randomized clinical trial with three parallel treatment groups, designed to compare the active treatment groups (CPAP and NSO) to the optimal medical management comparator (HLSE). Baseline data will be summarized using standard descriptive statistics for demographic and baseline clinical characteristics by treatment group. Based on our experience with the HeartBEAT Study, the rate of dropouts during the course of the three-month trial is expected to be low and we do not expect dropouts

to be differential with respect to treatment group assignment. The main analysis will include all subjects completing the follow-up examination. For the purposes of a sensitivity analysis, a result of “no change” will be imputed for all drop-outs, and compared to the main analysis.

The analysis for each of the primary outcome measures (LVEF and peak VO₂) will consist of a one-factor analysis of variance comparing the mean changes from baseline in LVEF (or VO₂). As we postulate similar benefits from CPAP and NSO, we will specify two contrasts: CPAP vs. HLSE and NSO vs. HLSE as our primary analyses. In a secondary analysis, we will also compare the effects of CPAP to NSO for the purpose of hypothesis generation for subsequent larger studies. This analysis is a simple analysis of variance, with data transformation or adoption of rank-based inference if approximate normality is not present. While the randomization should achieve approximate balance on potentially confounding conditions, analysis of covariance models that employ adjustments for recruitment site, age, sex, sleep apnea severity, comorbid illness, smoking and alcohol use will be fit to potentially improve the efficiency of the treatment effect estimates. Should a significant difference between treatment and comparator be identified, further exploratory analyses will assess the relation of adherence to therapy to change in outcome measures.

In order to compare the effectiveness of the assigned interventions in controlling sleep apnea over the course of the study, an additional exploratory analysis will compare the change in AHI, change in time in periodic breathing, and change in time at SpO₂ <90% between the baseline and final portable sleep monitoring studies. This analysis will utilize a one-factor analysis of variance. Further exploratory analyses will assess the relation of effectiveness of control of sleep apnea to changes in the primary outcome measures.

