1). We have used effect estimates based on the meta-analyzed mean effect sizes for CPAP and NSO included in the AASM Practice Parameters paper (41) of 6.4%, and 5.0% for CPAP and NSO, respectively, and an estimated SD of change in LVEF of 4.8% based on previous reports of the effect of either ASV, CPAP or NSO (40, 42, 45-47) on LVEF in patients with sleep apnea. We use the Bonferroni method to account for 2 main comparisons and perform the test comparing each treatment to control at a 2.5% significance level. Using a two-sided two-sample t-test, an evaluable sample size of 34 in the NSO (or CPAP) group and 17 in the HLSE group will achieve 90% power to detect a difference of 5.0% with a significance level of 2.5% assuming a standard deviation of 4.8% in each group, and 98% power to detect a difference in LVEF of 6.4%; there will be 80% power to detect a difference as small as 4.4% between either active treatment group and the HLSE group.

Changes in peak V02 (Aim 2) will be compared in a similar fashion as changes in LVEF. An evaluable sample size of 34 in CPAP or NSO group and 17 in HLSE group will have 80% power to detect a difference of 0.92 standard deviations with a significance level of 2.5% using a two-sided two-sample t-test. Only one study of treatment of central sleep apnea in HF reports the SD of change in peak VO₂, which was 2.5 ml/kg/min (58). The reported change in peak VO₂ with treatment of central sleep apnea with NSO was 1.4-5 ml/kg/min, with a median of 2.5 ml/kg/min (47, 50, 55, 58). The power for this Aim therefore appears adequate.

For the exploratory comparison of CPAP and NSO, the sample sizes of 34 evaluable subjects per group will provide 80% power to detect a difference of 3.3% in change in LVEF, assuming a SD of change of 4.8% and a two-sided significance level of 5%.

As comparisons for secondary outcomes (Aim 4) are exploratory in nature, they will be performed at 5% significance level without multiple comparison adjustment. For comparisons in a continuous outcome between each treatment group and the control group, an evaluable sample size of 34 in CPAP or NSO group and 17 in HLSE group achieve 80% power to detect a difference of 0.84 standard deviations with a significance level of 5% using a two-sided two-sample t-test.

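### Holm would be a cheap gain over the fixed 2.5% Bonferroni rule for the two primary contrasts; the present rule is valid but less powerful

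*Combined protocol and SAP*

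**What the plan says.** The Statistical analysis section sets a one-factor analysis of variance on change from baseline for each primary outcome (LVEF and peak VO2), and says "we will specify two contrasts: CPAP vs. HLSE and NSO vs. HLSE as our primary analyses". It attaches no multiplicity rule to those contrasts.

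The rule appears only under Sample size and power: "We use the Bonferroni method to account for 2 main comparisons and perform the test comparing each treatment to control", each "at a 2.5% significance level". The power statement there is for "Using a two-sided two-sample t-test, an evaluable sample size of 34 in the NSO (or CPAP) group and 17 in the HLSE group", with assumed effects "of 6.4%, and 5.0% for CPAP and NSO, respectively" and "assuming a standard deviation of 4.8% in each group". It claims 90% power at a difference of 5.0, 98% at 6.4 and 80% at 4.4. Peak VO2 is to be handled in the same way, also at 2.5% per contrast.

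Neither section provides a step-down, Dunnett or hierarchical procedure, and neither specifies confidence intervals.

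**The concern.** Under single-step Bonferroni each contrast must reach 2.5% whatever the other one shows. Once one contrast has been rejected at 2.5%, only one null hypothesis remains, and it can be tested at the full 5% without the familywise error exceeding 5%. Holm's procedure does exactly this. It rejects whenever Bonferroni rejects, and sometimes when Bonferroni does not.

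This plan is of the kind in which the second step is often reached. Both arms are expected to work, and the stated goal is to establish the efficacy of each. Under the planning effects CPAP is nearly certain to succeed, so oxygen, which has the smaller assumed effect, would almost always be tested at 5%. What is at stake is power for the second contrast, and hence the chance of a positive result for both treatments. The validity of the trial is not at stake.

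**Working it through.** **Inputs** (all from Sample size and power unless noted): evaluable n = 34 CPAP, 34 oxygen, 17 HLSE; SD of LVEF change 4.8; effects 6.4 and 5.0; two-sided 2.5% per contrast. A smaller CPAP effect of 2.2 comes from the multicentre trial described in the background section on positive airway pressure.

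**Step 1: reproduce the plan's power.**

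SE = 4.8 × √(1/34 + 1/17) = 1.426.

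Normal approximation: power = Φ(difference/SE − 2.241).

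- 5.0: Φ(3.507 − 2.241) = 89.7%
- 6.4: Φ(4.489 − 2.241) = 98.8%
- 4.4: Φ(3.086 − 2.241) = 80.1%

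With the two-sample t-test that the plan names (noncentral t, 49 df) the figures are 88.0%, 98.3% and 77.8%. With the pooled ANOVA error (82 df) they are 88.7%, 98.5% and 78.7%. The stated 90% is therefore reproduced by the normal approximation and is about 2 points high by the exact t-test.

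**Step 2: apply Holm.** A contrast is won if p ≤ 2.5%, or if p ≤ 5% and the other contrast has p ≤ 2.5%. The contrasts share the HLSE arm, so their correlation is (1/17)/(1/34 + 1/17) = 0.667. The results below come from simulated normal changes with at least one million trials per scenario, using two-sample t-tests. Each cell gives Bonferroni → Holm, in per cent.

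| True effects (CPAP / oxygen) | CPAP won | Oxygen won | Both won | At least one won |
|---|---|---|---|---|
| 6.4 / 5.0 (plan) | 98.3 → 98.7 | 88.0 → 92.8 | 87.5 → 92.6 | 98.8 → 98.8 |
| 5.0 / 5.0 | 88.0 → 91.3 | 88.0 → 91.3 | 81.4 → 88.1 | 94.6 → 94.6 |
| 4.4 / 4.4 | 77.8 → 82.5 | 77.8 → 82.5 | 67.7 → 77.1 | 87.9 → 87.9 |
| 2.2 / 5.0 | 23.1 → 32.6 | 88.0 → 88.1 | 22.9 → 32.5 | 88.1 → 88.1 |

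With pooled ANOVA error at the plan's effects, oxygen goes from 88.7 to 93.2 and both from 88.3 to 93.0. By the bivariate normal approximation, oxygen goes from 89.7 to 93.7. The oxygen gain is thus 4.0 to 4.8 points, depending on the method.

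**Step 3: error rates.**

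- No effect in either arm: the chance of any false rejection is 4.4% under both procedures.
- CPAP effective (6.4) and oxygen null: the chance of falsely declaring oxygen effective is 2.5% under Bonferroni and 4.8% under Holm. Oxygen is the only true null here, so 4.8% is also the familywise error, and it is below 5%.

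**The case against.** The strongest reply is that nothing is broken. Bonferroni is prespecified and valid, the trial was sized for it, and the stated 90% is reproduced by a standard approximation. That stands, and it is why this is offered as an improvement.

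It is also fair that the headline gain rests on a favourable assumption. The protocol itself cautions about the pooled CPAP estimate, raises possible publication bias, and reports only 2.2 in the multicentre trial. At that value oxygen gains almost nothing.

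A reader might infer four stronger things that the documents do not support:

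- **That the claimed 90% is an error.** It is 89.7% by the normal approximation. The lower figure of 88.0% appears only with the exact t-test.
- **That Holm lifts oxygen above 90% in general.** It does so at 6.4/5.0 and 5.0/5.0, but not if CPAP's effect is 2.2, where oxygen stays near 88% by t-test.
- **That the change costs nothing.** It needs no extra patients and keeps the familywise error within 5%. However, the false-positive rate for an ineffective arm nearly doubles when the other arm works, and a contrast won only at the second step (p between 2.5% and 5%) would have a 97.5% interval that includes zero.
- **That it settles multiplicity for the whole trial.** LVEF and peak VO2 are both primary. Holm within each outcome does not control error across the two. Holm over all four p-values would start at 5%/4 = 1.25%, stricter than the present 2.5%, so the gains shown here cannot be assumed to carry over.

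**Conclusion.** The point holds as an inexpensive efficiency improvement. At the planning values, Holm adds about 5 points to the power for oxygen (88.0% to 92.8%; 88.7% to 93.2% with ANOVA error) and about 5 points to the chance of winning both contrasts (87.5% to 92.6%). At 4.4/4.4 it takes per-contrast power from about 78% to 82%, past the 80% that the plan claims there.

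For oxygen the gain ranges from about 0.1 to 4.8 points over the CPAP effects examined. CPAP itself gains only about 0.3 points at 6.4, and roughly 9.5 points at 2.2, where it remains badly underpowered. The chance of at least one success is the same under both rules.

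These figures assume normally distributed changes, a common SD of 4.8 and the full evaluable numbers of 34/34/17. They concern LVEF only.

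**What to change.** In the Statistical analysis section, after the two contrasts are named, add a sentence to this effect: within each primary outcome, the CPAP-versus-HLSE and oxygen-versus-HLSE contrasts are tested by Holm's procedure at a familywise two-sided 5%, with the smaller p-value compared with 2.5% and, if it is significant, the other with 5%. Change the Bonferroni sentence under Sample size and power to agree. The single-step power figures can stay as a conservative basis for the sample size.

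If confidence intervals are to be reported, state their level and say that a contrast won only at the second step may have a 97.5% interval that includes zero. Say also that the procedure applies within each outcome and not across LVEF and peak VO2.

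The cost is one sentence plus the alignment, with no added patients or assessments. The change should be made before outcome data are seen by arm.

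### Three stated power figures for the primary outcomes are 1 to 2 points too favourable for the named t-test, and also for the planned ANOVA contrast

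*Combined protocol and SAP*

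**What the plan says.** All the inputs stand in the section Sample size and power. Each active arm is compared with HLSE, and a Bonferroni split leads the plan to "perform the test comparing each treatment to control at a 2.5% significance level". The method is given by the words "Using a two-sided two-sample t-test". The main claim is that "an evaluable sample size of 34 in the NSO (or CPAP) group and 17 in the HLSE group will achieve 90% power". It applies to a gap of 5.0 LVEF points at that level, and the spread of the changes is fixed by the words "assuming a standard deviation of 4.8% in each group". The same sentence adds "98% power to detect a difference in LVEF of 6.4" points, and ends by saying that "there will be 80% power to detect a difference as small as 4.4" points.

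For peak VO2 (Aim 2), the same group sizes and the same test are said to give "80% power to detect a difference of 0.92 standard deviations with a significance level of 2.5" percent.

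The section names no formula or software. The analysis itself is set out under Statistical analysis: a one-factor analysis of variance of change from baseline, with two contrasts, CPAP against HLSE and NSO against HLSE.

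**The concern.** A power statement that names its test, group sizes, level and SD should be reproducible from them. Three of the four figures for the primary outcomes are not, and all three err on the favourable side. With only 17 controls and a level of 2.5%, the difference between a t and a normal reference distribution shows in the first two digits of the power.

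At stake is the accuracy of the design claim. The 5.0-point difference is the planning effect for NSO, so the 90% figure is the stated power for one of the two primary contrasts. The 4.4-point and 0.92 SD figures tell the reader how small an effect the trial can reliably detect.

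**Working it through.** **Inputs** (Sample size and power, unless noted): n1 = 34 and n2 = 17 evaluable; SD = 4.8 LVEF points; two-sided level 0.025; differences of 5.0, 4.4 and 6.4 points, and 0.92 SD. From Statistical analysis: three arms in one ANOVA.

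**Common quantities**
- √(1/34 + 1/17) = 0.2970, so the standard error for LVEF is 4.8 × 0.2970 = 1.426 points.
- The noncentrality is the difference divided by its standard error: 5.0/1.426 = 3.507; 4.4/1.426 = 3.086; 6.4/1.426 = 4.489; 0.92/0.2970 = 3.097.

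**Step 1: the plan's own figures.** With a normal approximation, power = Φ(noncentrality − 2.241), where 2.241 is the 98.75th percentile of the standard normal distribution.
- 5.0 points: Φ(1.265) = 89.7%, stated 90%.
- 4.4 points: Φ(0.845) = 80.1%, stated 80%.
- 0.92 SD: Φ(0.856) = 80.4%, stated 80%.
- 6.4 points: Φ(2.247) = 98.8%, stated 98%.

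The first three agree to rounding. The fourth would round to 99%.

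**Step 2: the named test.** The pooled two-sample t-test has 34 + 17 − 2 = 49 degrees of freedom and a critical value of 2.312. Power is the probability that a noncentral t variable with 49 degrees of freedom exceeds 2.312 in absolute value.

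**Step 3: the planned analysis.** The ANOVA contrast uses the pooled error of all three arms: 34 + 34 + 17 − 3 = 82 degrees of freedom, critical value 2.283, same noncentrality.

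| Difference | Stated | Normal | t-test, 49 df | ANOVA contrast, 82 df |
|---|---|---|---|---|
| 5.0 points | 90% | 89.7% | 88.0% | 88.7% |
| 4.4 points | 80% | 80.1% | 77.8% | 78.7% |
| 0.92 SD | 80% | 80.4% | 78.1% | 79.0% |
| 6.4 points | 98% | 98.8% | 98.3% | 98.5% |

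A simulation of the t-test with 200,000 replicates gave 88.0% at 5.0 points and 77.9% at 4.4 points.

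**Step 4: detectable differences**, found by solving the same formulas for the difference.

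| Power | Stated | t-test | ANOVA contrast |
|---|---|---|---|
| 90%, LVEF | 5.0 points | 5.16 points | 5.10 points |
| 80%, LVEF | 4.4 points | 4.51 points | 4.46 points |
| 80%, peak VO2 | 0.92 SD | 0.940 SD | 0.930 SD |

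**Step 5: can rounding explain it?** Not for the named test. Just under 4.45 points, the top of the range that rounds to 4.4, the t-test has 78.8% power; just under 0.925 SD it has 78.6%.

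**Step 6: other variants.** A one-sided t-test at 0.025 and a two-sided t-test at 0.05 each give 93.0% and 85.7% at 5.0 and 4.4 points. Welch degrees of freedom give 87.0% and 76.5%. None matches the stated 90% and 80%.

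**The case against.** The strongest reply is that nothing depends on this. The sample size stays the same, and power at both LVEF planning effects (5.0 and 6.4 points) remains well above 80%. For peak VO2, the plan's own median change of 2.5 ml/kg/min with an SD of 2.5 is 1.0 SD, where the t-test has 85% power. The gap is also small beside the uncertainty in the SD: 4.65 instead of 4.8 would restore 90% at 5.0 points under the t-test, and 4.70 would do so under the ANOVA contrast. With full retention, 39 against 20 would give 92.8%. All of this stands, and it is why the point is minor.

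A second reply is that the ANOVA contrast, not a stand-alone t-test, is the planned analysis, and that it narrows the gap to between 1.0 and 1.3 points. That is right. Under that reading the two 80% figures lie at the edge of rounding: just under 4.45 points the contrast has 79.7% power, which itself rounds to 80%. But the text attributes its figures to the t-test, and at the differences as printed both readings fall short.

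The allowance for non-completion does not by itself close the gap. If the full 15% is lost, 39 falls to about 33 (39 × 0.85 = 33.15) and 20 falls to 17, and the t-test has 87.6% power at 5.0 points. Low dropout, which the plan expects, would close it: 36 against 18 evaluable gives 90.0% at 5.0 points and 80.4% at 4.4 points.

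A reader might infer that a normal approximation was used in place of the t-test. Three figures fit that, but the documents name no formula, and other figures point elsewhere. The 98% at 6.4 points fits the t-test (98.3%) better than the normal formula (98.8%). So does the 80% claimed at 0.84 SD for secondary outcomes at the 5% level: 79.2% by the t-test, 80.7% by the normal formula. The origin remains an inference, and the discrepancy does not depend on it.

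**Conclusion.** The discrepancy is real but minor. On the plan's own inputs, the stated 90%, 80% and 80% should read 88.0%, 77.8% and 78.1% for the named t-test, or 88.7%, 78.7% and 79.0% for the planned ANOVA contrast. In detectable differences at 80% power, the t-test moves LVEF by about 0.1 points (4.4 to 4.51) and peak VO2 by 0.02 SD (0.92 to 0.94).

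This rests on normally distributed changes, a common SD of 4.8 for LVEF, exactly 34 and 17 evaluable patients, and a two-sided 2.5% level, all taken from the plan except normality, which the t-test presumes.

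Two stronger readings are not supported. The trial is not shown to be underpowered or its sample size wrong, since power at the planning effects stays close to what was claimed. Nor is the whole section wrong: the 98% figure is correct for the t-test, and the two 80% claims at the 5% level are nearly right under it (79.2% at 0.84 SD, and 79.8% at 3.3 points for CPAP against NSO).

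**What to change.** Keep the sample size and restate three figures in Sample size and power. One of two versions will do:

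- **If the t-test stays as the stated basis:** about 88% power at 5.0 points, 80% power at 4.5 points, and 80% power at 0.94 SD for peak VO2. The 98% at 6.4 points can stay.
- **If the figures are meant for the ANOVA contrast:** say so, and state about 89% power at 5.0 points, 80% power at 4.5 points, and 80% power at 0.93 SD for peak VO2. The figure at 6.4 points is then 98.5%.

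Naming the formula or software would let a reader reproduce the figures. The cost is a few words and three numbers, with no added patients and no change to the analysis. The downside is that the stated figures become slightly less favourable.
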